We will enroll all primary care physicians and their eligible patients. Eligible patients include adults ≥ 18 years and < 85 years with a diagnosis of diabetes, hypertension, or hyperlipidemia; evidence of poor or worsening disease control (see Table 1); and evidence of medication non-adherence based on medication refill data. Disease control is evaluated using the most recent lab or blood pressure values in the electronic health record and is based on clinical guideline targets from the American Diabetes Association (ADA), the Eighth Joint National Committee (JNC 8) hypertension guidelines, and the American College of Cardiology/American Heart Association (ACC/AHA) cholesterol guidelines. Adherence is assessed using prescription claims data. HVMA prescription data are available with a one-month lag. For each medication used to treat any one of the targeted conditions, the proportion of days covered (PDC) is calculated as the number of days of medication that a patient filled between the first fill date and the randomization date divided by the number of days in that same period (up to a maximum of 365 days). We consider drugs that are chemically related and not intended for use in combination to be interchangeable (e.g., two different statins). We average the PDC for all medications used to treat a single condition (e.g., all oral hypoglycemics) and then calculate an overall average adherence for all of the conditions that a patient had at the time of their identification.

TABLE 1. Definitions of poor and worsening disease control

Condition	Age (years)	Poor control	Worsening control
Diabetes	...	Latest HbA1c > 8	Latest HbA1C $7.5 \leq \text{to} \leq 8$, and previous HbA1C 1% lower
Hypertension	≥ 60	Latest BP $> 150/90$	Latest BP $140/80 \leq \text{to} \leq 150/90$, and previous BP 20 mmHg lower
	< 60	Latest BP $> 140/90$	Latest BP $130/80 \leq \text{to} \leq 140/90$, and previous systolic or diastolic BP 20 mmHg lower
Hyperlipidemia	...	Diagnoses of ASCVD	...
	40-75	Type 1 or 2 diabetes and use of glucose lowering agent	...
	40-79	ASCVD risk $> 7.5\%$...
	...	LDL $> 190 \text{ mg/dl}$	Latest LDL $175 \leq \text{to} \leq 190$, and previous LDL 30 mg/dl lower

...= N/A; Abbreviations: HbA1c, glycosylated hemoglobin; BP, blood pressure; ASCVD, atherosclerotic

cardiovascular disease; LDL, low-density lipoprotein

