To identify individuals who would benefit most from the intervention, a patient is defined as being non-adherent if they (1) have been less than 80% adherent to the specific class of medications used to treat the condition(s) for which they were being identified as being poorly controlled and (2) if their “average of averages” PDC for all eligible study drugs is less than 80%. For example, patients with poorly

controlled diabetes who are non-adherent to their diabetes medications but adherent to their statins and antihypertensives, would only be eligible if their average adherence across all 3 conditions is less than 80%. Patients are excluded if, prior to randomization, they have less than 6 months of continuous enrollment in the health plan (to allow adequate assessment of eligibility), are < 18 or > 85 years of age, or have no available telephone contact information, which would preclude contact for enrollment and delivery of the intervention.

Study procedures

Once identified, PCPs of potentially eligible intervention group patients will be sent a secure message using the electronic health record to ask permission to include their patient(s) in the study. If a physician does not explicitly respond to approve or disapprove of the identified patient(s) to participate in the study within 5 days, they are sent a reminder message; one day later, their patients will automatically be opted in to the study.

Patients approved for enrollment in the study are sent a letter informing them about the study along with a simple, one compartment per day, pillbox that allows for the storage of one week of medication. Patients are then contacted by telephone to schedule a phone consultation with the clinical pharmacist. At this time, they are also administered the Patient Activation Measure (PAM), a questionnaire to assess the knowledge, skills, and confidence to manage one's health and health care. The PAM is subsequently used to tailor the intervention for that individual patient.

Intervention

The central component of the multi-faceted intervention is an individually-tailored telephone consultation conducted by a clinical pharmacist who is part of the Harvard Vanguard care team. The

clinical pharmacists work at multiple sites; in order to reduce the chances of contamination, they are restricted to providing clinical services only at other intervention sites during the time period of this study.

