The trial's primary outcome is medication adherence assessed at 12 months after randomization. For this outcome, medication adherence will be assessed using prescription claims data and measured as the mean PDC over the 12 months after randomization using the "average of averages" approach used for study eligibility. Adherence will be measured only for medications that qualified a patient for inclusion in the study and follow-up will begin at the point of randomization. Medications that were filled before randomization but had a supply that extended into the follow-up period will have their carry-over supply included in the adherence calculation.

In sensitivity analyses, we will measure medication adherence by calculating PDC beginning from the first fill of a medication after randomization until the end of the 12-month follow-up period. We will also repeat our analyses censoring patients with diabetes when they initiate insulin.

The secondary outcomes for the study include disease control and rates of healthcare utilization. Disease control will be measured as the following two different outcomes: (1) the proportion of patients achieving good disease control for all of their eligible conditions and (2) the proportion of patients achieving good disease control for at least one of their eligible conditions. Because disease control will be evaluated using biometrics that are collected during routine care rather than at study-prescribed intervals, we will use those values that are closest to each patient's 12-month end of follow-up period. If more than 10% of subjects have missing data we will repeat our analyses using multiple imputation

Rates of healthcare utilization will also be measured using administrative claims data and will include all-cause emergency room visits, physician office visits, and all-cause hospitalizations during the 12-month follow-up period.

Analytic plan

We will report the means and frequencies of pre-randomization variables separately for intervention and control subjects. Comparisons of these values will be performed using t-tests and chi square tests and their non-parametric analogs, as appropriate. The outcomes will be evaluated using intention-to-treat principles among all randomized patients.

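### The insulin sensitivity analysis ends the whole patient's follow-up at insulin start, although only the oral-hypoglycemic component of adherence needs to end

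*Combined protocol and SAP*

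**What the plan says.** The final protocol (Outcomes) defines primary adherence as the "mean PDC over the 12 months after randomization using the 'average of averages' approach used for study eligibility", and adds: "Adherence will be measured only for medications that qualified a patient for inclusion in the study". The averaging is set out under Subjects: "We average the PDC for all medications used to treat a single condition (e.g., all oral hypoglycemics) and then calculate an overall average adherence". The worked example there shows that one patient can carry several classes, since such a patient "would only be eligible if their average adherence across all 3 conditions is less than 80" percent.

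Outcomes then lists two sensitivity analyses. The first starts the PDC at the first fill after randomization. The second reads: "We will also repeat our analyses censoring patients with diabetes when they initiate insulin". Nothing limits it to the glucose-lowering class, or to patients whose glucose-lowering drugs count in their outcome.

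The primary analysis is by intention to treat in all randomized patients and has no insulin rule. The final analysis plan (Outcome Measures; Statistical analyses) does not mention insulin, so nothing there narrows the protocol's sentence.

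**The concern.** The aim is sensible. If a patient moves from tablets to insulin, the missing tablet refills look like non-adherence. But that affects one component of the average. Statin and antihypertensive fills keep their meaning after insulin starts and stay visible in claims. Censoring the patient ends those components too.

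The cut also falls at an event after randomization. The final protocol (Intervention) has pharmacists work with primary care physicians on a plan for adherence and disease control and recommend therapy changes, so the intervention might alter whether or when insulin starts. That is an inference.

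A sensitivity analysis should vary one thing. This one varies two: how the oral-agent component is handled, and how long the other classes are followed. If it disagreed with the primary result, a reader could not tell which change was responsible. It is also the only analysis in the plan that addresses insulin.

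**Working it through.** **Yardstick.** The plan gives no figure for this analysis. The only relevant one is the 2.5-point target (final protocol, Sample size considerations). Its sample size reproduces: with SD 0.25 and a two-sided 5% level (assumed; not stated), 2 × (1.960 + 0.842)² × (0.25/0.025)² ≈ 1,570 per arm, or 3,140. Then 3,140 × 1.10 = 3,454, and 3,454 / 0.85 ≈ 4,064, against the stated 4,000. Nothing below depends on this.

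**1. Follow-up removed.** Take a patient with three counted classes who starts insulin on day t. Patient-level censoring drops 2 × (365 − t) of the 730 statin and antihypertensive class-days.

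| Start | Dropped | Share |
|---|---|---|
| Day 91 | 2 × 274 = 548 | 75% |
| Day 182 | 2 × 183 = 366 | 50% |
| Day 273 | 2 × 92 = 184 | 25% |

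Ending only the oral-agent component drops none. This step needs no assumption about adherence.

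**2. Effect on one patient's value.** Assume all three classes have PDC p₁ before insulin, the other two have p₂ after it, oral agents stop at insulin start, and PDC is computed over the observed window. Let O = [p₁t + p₂(365 − t)]/365.

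- Patient-level value: p₁
- Class-level value: (p₁ + 2·O)/3

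For t = 182:

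| p₁ then p₂ | Patient-level | Class-level | Difference |
|---|---|---|---|
| 0.50 then 0.70 | 0.500 | (0.500 + 2 × 0.600)/3 = 0.567 | −0.067 |
| 0.60 then 0.60 | 0.600 | 0.600 | 0 |
| 0.70 then 0.50 | 0.700 | (0.700 + 2 × 0.600)/3 = 0.633 | +0.067 |

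For the two changing patterns the gap is ±0.100 at day 91 and ±0.034 at day 273. The sign follows the adherence trend, which the documents do not give.

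In the constant case the uncensored primary value is (0.60 × 182/365 + 0.60 + 0.60)/3 = 0.500. So the insulin problem is real, and ending the oral-agent component alone already restores 0.600.

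**3. Trial-wide size.** The documents give neither the share of patients with diabetes nor an insulin-start rate. Assume 30–50% have diabetes, 3–10% of them start insulin, and starts are spread evenly over the year.

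- Patients affected, of 4,076: 4,076 × 0.30 × 0.03 ≈ 37 to 4,076 × 0.50 × 0.10 ≈ 204.
- Non-diabetes class-time lost: 0.30 × 0.03 × 0.5 = 0.45% to 0.50 × 0.10 × 0.5 = 2.5%.
- Shift in the arm difference, if start rates among patients with diabetes differ by 2–5 percentage points and each starter's value moves by 5–10 points: 0.30 × 0.02 × 5 = 0.03 to 0.50 × 0.05 × 10 = 0.25 points, or about 1% to 10% of 2.5.

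The last line counts only a difference in how many patients start. Different adherence trends by arm could also cause a shift; that is not sized here.

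**The case against.** The best defence is that this is one short sentence about a sensitivity analysis, perhaps shorthand for ending the oral-agent window. No primary or secondary result depends on it. The limited reach stands and keeps the point modest. The shorthand reading is possible, but the text does not say it, and an analyst following the words would censor the patient.

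The link to the intervention is also inferred. The only therapy change given as an example is a brand-to-generic switch. That stands, but the loss of follow-up in step 1 does not depend on it.

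Several stronger readings are tempting and are not supported:

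- **The rule favours the arm with more insulin starts.** This needs adherence to fall over time. If it rises, the sign reverses; if it is flat, there is no shift. Nor does the carry-over rule settle it ("Medications that were filled before randomization but had a supply that extended into the follow-up period will have their carry-over supply included"): that is supply in hand, credited in both arms, and the companion sensitivity analysis already varies how follow-up begins.
- **The bias could approach a third of the target.** Suppose a patient starts insulin at month 3, with oral agents at 90% until then and the other classes at 85% in months 1–3 and 60% over the year. The two methods give (90 + 85 + 85)/3 = 86.7 and (90 + 60 + 60)/3 = 70.0. A 5-point arm difference across all patients then yields 16.7 × 0.05 = 0.83 points. But this implies (60 × 12 − 85 × 3)/9 = 51.7% in months 4–12, and a 10- to 17-point difference in starts among patients with diabetes (5/0.50 to 5/0.30). Those inputs are extreme.
- **Patients whose outcome contains no oral hypoglycemic are certainly cut off.** Table 1 does admit patients under hyperlipidemia through "Type 1 or 2 diabetes and use of glucose lowering agent". Whether their oral agents count depends on whether qualifying medications means the drugs for the poorly controlled condition or every study drug in the average.
- **Patients already on insulin at randomization should lose their oral-agent component.** The documents do not say that oral-agent fills lose meaning in such patients. Dropping them could discard valid data and leave some randomized patients with no outcome.

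**Conclusion.** The concern holds as a specification fault in a sensitivity analysis. Read literally, the rule removes statin and antihypertensive follow-up that insulin does not disturb: 25% to 75% of those class-days for starts between day 273 and day 91. It therefore cannot isolate the effect of insulin handling.

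The direction of any shift is unknown. A size of about 0.03 to 0.25 points rests on assumed diabetes shares, insulin-start differences and adherence changes. It would not by itself overturn a 2.5-point effect. A reader should not infer that the primary comparison is affected; it is not.

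**What to change.** Replace the sentence in the final protocol (Outcomes) with wording such as:

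> In a sensitivity analysis, where oral hypoglycemics count in a patient's outcome, that component ends at the first insulin fill after randomization. Statin and antihypertensive components continue to month 12. Patients without a counted oral hypoglycemic are unaffected. The number starting insulin is reported by arm.

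Add the same text to the final analysis plan. Make no change for patients already on insulin at randomization.

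The cost is one short passage in each section and minor programming, with no new data. One limitation remains: the diabetes component is still shortened at an event after randomization, and a patient whose only counted class is oral hypoglycemics is handled as now. For everyone else the distortion is confined to that component, and insulin starts by arm let readers judge it.

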Highly effective medications to treat and prevent the complications of chronic disease have been developed and evaluated. While rates of prescribing effective therapies have improved substantially, long-term adherence remains exceptionally poor. Nearly 50% of patients become non-adherent within a year of treatment initiation. Interventions that succeed in improving medication adherence may confer important clinical benefits across large populations, and may even be cost-saving by reducing rates of costly clinical outcomes such as myocardial infarction and stroke.

The success of interventions to improve adherence has been relatively limited, either because of the nature of the intervention or their broad applications to patients who do not require them or will not benefit from them. Prior studies have also been limited by recruiting small samples of volunteers, following patients for short periods, and not evaluating their impact on clinical outcomes. The efficacy of future efforts is likely to be increased by targeting interventions to patients demonstrating both poor adherence and poor disease control, tailoring interventions to individual patient needs, and touching larger and more representative patient populations and care settings. These goals can be achieved by the innovative use of information technology including electronic health records (EHR) and other advanced communication technologies, including texting.

We propose a cluster randomized controlled trial (RCT) of a novel tele-pharmacist based intervention to improve adherence to medications for hypercholesterolemia, hypertension, and diabetes. We will evaluate an innovative intervention that uses of EHR data to identify 4076 adult patients cared for by approximately 150 primary care physicians who are both non-adherent and not achieving recommended clinical targets for glycemic, blood pressure, and cholesterol control in a real-world primary care setting. Following EHR-facilitated referral from the treating primary care physicians, a clinical

pharmacist will direct an outreach program using multiple communication technologies including a telephone consultation, text messaging and video visits to improve medication adherence.

Study setting

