This trial is being conducted at Harvard Vanguard Medical Associates (Harvard Vanguard), which is a practice of Atrius Health, a large multispecialty medical group and a Pioneer Accountable Care Organization. Harvard Vanguard employs approximately 150 primary care physicians (PCPs) who provide care for approximately 300,000 adult patients at 17 practice sites. Of these, 15 practice sites have integrated retail pharmacies, where approximately 50% of patients obtain their prescription medications. Within each site, all PCPs and their eligible patients will be randomized to the same study arm.

Study design and randomization

STIC2IT is a pragmatic, prospective, intention-to-treat, cluster-randomized controlled trial designed to test the impact of a technologically-enabled, behaviorally-targeted pharmacist intervention designed to improve medication adherence and disease control among the specific group of individuals who are most likely to benefit from this intervention – those who are non-adherent to their glucose lowering, anti-hypertensive, or statin medications and have evidence of poor disease control based on recommended clinical targets. We randomly selected 1 of the 15 Harvard Vanguard practice sites with onsite pharmacies as a pilot site for intervention refinement. The remaining 14 Harvard Vanguard practice sites were then cluster-randomized such that all PCPs and their patients in a given practice site were assigned to the same study arm. Because the practice sites differ from each other, simple cluster randomization may have resulted in imbalances in patient or provider factors that could potentially bias outcome assessment. Therefore, we categorized the practice sites based on their size (i.e., small or large, based on the number of patients receiving care at each site) and whether clinical pharmacists at the sites

offered disease management counseling directly to patients (i.e., yes or no). Within the resultant 4 blocks, practices were then randomized in a 1:1 ratio to intervention or control using a random number generator.

Subjects

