In the primary analysis, the outcomes will be compared using generalized estimating equations with an identity link function and normally distributed errors to account for the clustering of subjects within practice sites. Our primary models will also adjust for the block-randomized design. If there are differences in baseline characteristics between study groups that are believed to be confounders of the intervention–outcome association, we will repeat our analyses after adjusting for these covariates.

A similar approach will be taken for the analysis of the secondary outcomes, except using logit link functions with binary errors and log link functions with Poisson errors, as appropriate for disease control and rates of healthcare utilization, respectively.

Several additional analyses will also be conducted. First, we will assess the correlation between calculated adherence based on insurer claims, self-reported adherence, and pharmacy transaction records (for patients filling prescriptions at Harvard Vanguard pharmacies). Second, we will use Markov modeling to assess the long-term impact of the intervention on cost, quality-adjusted survival, and cost-effectiveness of the intervention.

Sample size considerations

Our study should be sufficiently powered to detect small, clinically meaningful changes in the primary outcome. We powered the study to detect a 2.5% mean change in adherence between the intervention and control groups, assuming a standard deviation of 0.25 (a conservative assumption), clustering at the practice level with a design effect of 1.10, and a 15% non-differential loss to follow-up

rate. We assumed that 95% of potentially eligible intervention patients would be approved for study inclusion by their PCPs and that 50% of these patients would agree to a pharmacist consultation. With these assumptions, we estimated that we would need a total sample size of 4000 eligible patients to provide more than 80% power to detect differences in our primary study outcome of medication adherence. In other words, if those patients receiving the intervention demonstrate a 4.6% improvement in adherence, we will still have more than 80% power to detect an improvement of 2.5% in the overall sample. We also have substantial power to detect improvements in disease control, assuming a rate of controlled disease of 30% based on our pilot data.

Summary of changes to protocol

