The independent variable of interest is exposure to the pharmacist intervention. We will measure several variables to assess the degree of balance between patients and physicians randomized to intervention versus control, to adjust for chance imbalances, and to assess whether the efficacy of the intervention is modified by particular patient characteristics. Patient demographic characteristics and major comorbid conditions, as identified based on EHR data, will be included as independent variables

HVMA currently has an existing clinical pharmacy program. These clinical pharmacists already work collaboratively with the primary care physicians in the clinics to provide patient education and advice around medication management. Primary care physicians can currently refer patients to the clinical pharmacist using an electronic referral in the electronic health record.

Final analysis plan

Sample size considerations

Our study should be sufficiently powered to detect small, clinically meaningful changes in the primary outcome. We powered the study to detect a 2.5% mean change in adherence between the intervention and control groups, assuming a standard deviation of 0.25 (a conservative assumption), clustering at the practice level with a design effect of 1.10, and a 15% non-differential loss to follow-up rate. We assumed that 95% of potentially eligible intervention patients would be approved for study inclusion by their PCPs and that 50% of these patients would agree to a pharmacist consultation. With these assumptions, we estimated that we would need a total sample size of 4000 eligible patients to provide more than 80% power to detect differences in our primary study outcome of medication adherence. In other words, if those patients receiving the intervention demonstrate a 4.6% improvement in adherence, we will still have more than 80% power to detect an improvement of 2.5% in the overall sample. We also have substantial power to detect improvements in disease control, assuming a rate of controlled disease of 30% based on our pilot data.

Outcome Measures

Primary outcome - Adherence

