The trial's primary outcome is medication adherence assessed at 12 months after randomization. Medication adherence will be assessed using prescription claims data and measured as the mean PDC over the 12 months after randomization using the "average of averages" approach used for study eligibility. Adherence will be measured only for medications that qualified a patient for inclusion in the study and follow-up will begin at the point of randomization

Secondary outcomes

The secondary outcomes for the study include disease control and rates of healthcare utilization.

Disease control will be measured as the following two different outcomes: (1) the proportion of patients achieving good disease control for all of their eligible conditions and (2) the proportion of patients achieving good disease control for at least one of their eligible conditions. Because disease control will be evaluated using biometrics that are collected during routine care rather than at study-prescribed intervals, we will use those values that are closest to each patient's 12-month end of follow-up period up to a maximum of 15 months after randomization

Rates of healthcare utilization will also be measured using administrative claims data and will include all-cause emergency room visits, physician office visits, and hospitalizations during follow-up

Statistical analyses

We will report the means and frequencies of pre-randomization variables separately for intervention and control subjects. Comparisons of these values will be performed using t-tests and chi square tests and their non-parametric analogs, as appropriate. The outcomes will be evaluated using intention-to-treat principles among all randomized patients. In the primary analysis, the outcomes will be compared using generalized estimating equations with an identity link function and normally distributed errors to account

for the clustering of subjects within practice sites. Our primary models will also adjust for the block-randomized design. If there are differences in baseline characteristics between study groups that are believed to be confounders of the intervention–outcome association, we will repeat our analyses after adjusting for these covariates.

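### The primary GEE on 14 randomized sites names no small-sample method; the usual sandwich z-test would reject a true null about 15% of the time at an assumed two-sided 5%.

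*Combined protocol and SAP*

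**What the plan says.** The final protocol (Study design and randomization) sets one site aside as a pilot, then states "The remaining 14 Harvard Vanguard practice sites were then cluster-randomized". Sites were classified by whether their clinical pharmacists counsel patients directly and by size, "small or large, based on the number of patients receiving care at each site". Allocation followed: "Within the resultant 4 blocks, practices were then randomized in a 1:1 ratio to intervention or control".

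The Analytic plan of the final protocol and the Statistical analyses section of the final analysis plan compare the primary outcome by "generalized estimating equations with an identity link function and normally distributed errors to account for the clustering of subjects within practice sites", and add "Our primary models will also adjust for the block-randomized design". Both carry a similar approach to the secondary outcomes, with a logit link for disease control and a log link for utilization.

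Sample size considerations allow for "clustering at the practice level with a design effect of 1.10, and a 15% non-differential loss to follow-up", and conclude that the trial needs "a total sample size of 4000 eligible patients to provide more than 80% power to detect differences in our primary study outcome". The Background of the final protocol plans to "identify 4076 adult patients cared for by approximately 150 primary care physicians".

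Nowhere do the final texts give alpha or sidedness, working correlation, type of standard error, reference distribution, degrees of freedom, block coding or a small-sample correction. The initial protocol randomized physicians (about 170 clusters). The change to sites left a GEE in place with 14 clusters and added no safeguard.

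**The concern.** The sandwich variance with a normal reference relies on a large number of clusters. Here there are 14, and the block-adjusted model spends several site-level parameters on them. The uncorrected standard error is then too small and the normal critical value too low. Both errors favour rejection.

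This is the trial's primary test. If it is run on software defaults, a null intervention is declared effective about three times as often as intended. The same data can also cross or miss significance according to choices that the plan leaves open, so those choices could be made after the results are known. The power statement is affected too, because it makes no allowance for the small number of sites.

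**Working it through.** **Inputs from the documents.** 14 sites; 4 blocks; 1:1 allocation; difference 0.025; SD 0.25; design effect 1.10; 15% loss; 4000 patients (4076 in the Background).

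**Assumed, because the documents do not give them.** Two-sided alpha of 5%; sites per block; the spread of site sizes; an uncorrected sandwich with z as the default analysis.

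**1. The plan's own figure.** Patients per arm = 2 × (1.960 + 0.842)² × 0.25² / 0.025² = 1570, or 3140 in total. Then 3140 × 1.10 / 0.85 = 4064, within 2% of 4000. In the other direction:
- Effective patients per arm at 4000 = 2000 × 0.85 / 1.10 = 1545.5.
- SE = 0.25 × √(2/1545.5) = 0.00899, and 0.025/0.00899 = 2.78.
- Power with a normal reference is 79.4%; at 4076 it is 80.1%.

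The sample size therefore reproduces, with power at the 80% line rather than clearly above it.

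**2. Degrees of freedom.** Intercept, treatment and three block terms make 5 site-level parameters, so 14 − 5 = 9. If the two block factors enter as main effects only, 14 − 4 = 10.

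**3. Type I error of the default, equal sites.** The uncorrected sandwich divides by 14 instead of df, so the rejection rate is 2 × P(t_df > 1.96 × √(df/14)).
- 9 df: 1.96 × √(9/14) = 1.571, giving 15.1%. Interval coverage is 84.9%, and the interval is 1.571/2.262 = 69% as wide as the t interval.
- 10 df: 1.96 × √(10/14) = 1.656, giving 12.9%.
- A t reference on 9 df without bias correction: 2 × P(t₉ > 2.262 × √(9/14)) = 10.3%.

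**4. Unequal sites.** The null was simulated with 3400 analysed patients, SD 0.25, independence working correlation and several block layouts. The ICC was 0.1/(3400/14 − 1) = 0.00041, which is what a design effect of 1.10 implies. Size CVs ran from 0 to 0.8.

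| Method, nominal 5% | Rejection of a true null |
|---|---|
| Sandwich, z, four block levels, unequal sites | 14.6%–18.9% |
| Sandwich, z, two main effects | 12.4% (equal sites), 15.2% (CV 0.6) |
| Kauermann-Carroll, t on 9 df* | 4.7%–5.4% (equal), 4.8%–8.6% (unequal) |
| Mancl-DeRouen, t on 9 df* | 1.6%–4.0% |
| Permutation within blocks* (even layouts only) | 3.1%–6.0% |

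*These ranges also include runs at an assumed ICC of 0.01.

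At ICC 0.01 (design effect about 3.4) the sandwich z-test with four block levels gives 14.6%–21.5%.

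**5. Power with 14 sites respected.** The noncentral t with 2.78 gives 69.7% on 9 df and 70.8% on 10 df at 4000 patients, and 70.5% and 71.6% at 4076. On 9 df, 80% power needs a difference of about 2.8 points, or about 5,140 patients with the design effect held at 1.10. If the implied ICC is held instead, the design effect grows with site size and the figure is about 5,280.

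**6. Secondary models (illustrative).** With assumed between-site SDs and utilization means, the default z-test rejects 14.3%–17.2% of the time for the logit model at 30% control, and 14.2%–19.1% for the log-link model.

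**The case against.** The strongest reply is that the 15% belongs to a method the plan never names. A model-based exchangeable standard error with z also fits the wording. At the plan's design effect it rejects only 5%–7% of the time if negative estimated correlations are set to zero. That is correct, and it makes the defect one of under-specification. It does not remove the problem. The same estimator gives 14%–21% if negative correlations are allowed, and at the plan's design effect the estimate was negative in 82%–88% of four-level runs. At an assumed ICC of 0.01 it gives 14%–18% even with truncation.

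A second reply is that a design effect of 1.10 leaves little clustering to mishandle. This does not help the sandwich, which estimates variance from 14 site residuals whatever the true ICC. Its error stayed at 15%–18% for design effects from 1.0 to 4.

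Third, the rates for unequal sites rest on assumed sizes and layouts. This stands. Nor is 19% a ceiling: with an exchangeable correlation free to go negative and unequal sites, the sandwich z-test reached about 28%.

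Fourth, the loss of power follows from the remedy chosen. That is also true, but the z-based figure is available only with a test whose error rate is not controlled.

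**Conclusion.** The concern holds and should be fixed before the analysis. The omission is plain from the text. An ordinary reading of the plan gives about 15% type I error with equal sites and four block levels (12.9% with two main effects). With independence working correlation at the plan's design effect, the overall range is about 13% to 19%. The equal-site figure needs only the assumed two-sided 5% and the default estimator, so confidence in it is high. Confidence in the unequal-site rates is moderate, because they depend on block layouts and size spreads that the documents do not report. The claim of more than 80% power is borderline at 4000 patients with z, and falls to about 70% with t on 9 df.

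**What to change.** In the final analysis plan, before outcome data are seen:

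- State alpha and sidedness, the working correlation (including how negative estimates are handled), and whether the blocks enter as four levels or two main effects.
- Name one method for primary inference. The first option is a permutation test that follows the actual within-block allocation, including any block with an odd number of sites, with the interval by test inversion. The second is a bias-corrected sandwich with a t reference on sites minus site-level parameters (9 or 10 df).
- If the second is chosen, weigh the correction against the actual site sizes. Kauermann-Carroll can stay mildly inflated when sizes differ widely (up to 8.6% here, and about 12% with an unrestricted exchangeable fit). Mancl-DeRouen held its level but costs the most power.
- Apply the same rule to the logit and log-link models.
- Restate power under the chosen method in both Sample size sections.

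The cost is SAP text and a short program, with no new data. Intervals widen and stated power falls. Simulated at the plan's design effect, power is 65%–70% with Kauermann-Carroll and t on 9 df, 59%–68% with permutation, and 42%–51% with Mancl-DeRouen and t on 9 df. The lower ends apply when site sizes are more unequal.
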